1.1 DEFINITIONS OF TERMS USED IN STUDY

A table of terms, their acronyms, and definitions are provided for the protocol that follows.

Construct	Term (acronym)	Definition
Groups participating in study	Site	A Home and Community Based Services Provider under contract with the State of MI to provide MiChoice services in the Medicaid program.
	Clinician	A Home and Community Based Services provider employee who is a clinician that provides either care to beneficiaries or a supervisor who oversees clinician care and is an RN, SW, OT.
	Beneficiary	A person who is a Medicaid recipient of care and services in the Home and Community Based Services.
Components implemented in study	Community Aging in Place, Advancing Better Living for Elders (CAPABLE)	Evidence-based intervention implemented in the Home and Community Based Services program in Michigan.
	MiCAP	A package of implementation strategies that will be used to implement CAPABLE in the Home and Community Based Services in Michigan in this project.
	External facilitator (EF)	A supervisor at a Home and Community Based Services program site in Michigan where we performed our prior work and who was an early adopter of CAPABLE and will guide the work of IFs (e.g., fidelity to CAPABLE, engaging clinicians for training, understanding the benefits of CAPABLE) in one arm of the study.
	Internal facilitator (IF)	A supervisor at a Home and Community Based Services program site in Michigan who will be trained and will facilitate and lead the CAPABLE implementation, and oversee clinician training and performance of CAPABLE; and oversees the provision of usual “waiver” care.
	Interdisciplinary Coordination (IDC)	Coordination between and among the RN, OT, and SW during the performance of CAPABLE to assure the beneficiary’s person-centered service plan is enacted as desired.
	Occupational Therapist (OT)	Clinician who is licensed as an OT.
	Registered Nurse (RN)	Clinician who is licensed as an RN.
	Social Worker (SW)	Clinician who is licensed as an SW.
	Center for Information Management (CIM)	Software company that houses the electronic health record for beneficiaries in the waiver program.
Organizations associated with study	Center for Medicare and Medicaid Services (CMS)	Oversight body of all Medicaid and Medicare programs.
	Institutional Review Board (IRB)	Human Subjects oversight board.
	Grand Valley State University (GVSU)	University
	Michigan Department of Health and Human Services (MDHHS)	The oversight organization of Medicaid programs for the State of Michigan.
	National Institute on Aging (NIA)	Grant funder.
	Activities of daily living (ADL)	Activities such as bathing, walking, transfers that are performed to carry out daily living.
General terms used in study	Blackboard (Bb)	Software used to house training modules.

	Continuous Quality Assessment Review (CQAR)	Quality review process for Medicaid waiver program.
	Electronic health record (EHR)	Electronic record where beneficiaries care is documented.
	HIPAA	Health Insurance Portability and Accountability Act
	Instrumental activities of daily living (IADL)	Activities such as shopping, banking, and cleaning that are performed to carry out daily living.
	Michigan (MI)	A state.
	Person Centered Service Plan (PCSP)	Plan of care for waiver beneficiaries in the electronic health record.
	Progress Note (PN)	Notation of care in the electronic health record.
	Self-efficacy (SE)	A feeling of worth or self-esteem.
Study team at university	Primary Investigator (PI)	Investigator is the PhD trained scientist to be responsible for conducting trial and assuring all approvals, compliance requirements, and assurances are met according to NIH expectation. ([name])
	Project Manager (PM)	The PM assists the PI in performing responsibilities for conducting trial and assuring all approvals, compliance requirements, and assurances are met in accordance to NIH expectation. ([name])
	Research Assistant (RA)	A GVSU student (required in AREA grant funded projects) who is a research team member.
Tools used in study	EBPAS	Evidence-Based Practice Attitude Scale
	GSE	General Self-efficacy
	ILS	Implementation Leadership Scale
	MDS	Minimum Data Set for Home Care Tool
	ORCA	Organization Readiness to Change
	SIC	Stages of Implementation Completion

1.2 BACKGROUND AND SIGNIFICANCE

There are 39 million Americans over age 65;¹⁻² and 42% of older adults report problems with function, which can lead to difficulty with activities of daily living (ADLs),³ falls and nursing home placement.⁴ Consequently, implementing evidence-based models focused on aging-in-place in older adults is a public health priority. One evidence-based model is Community Aging in Place, Advancing Better Living for Elders (CAPABLE).⁶⁻⁹ CAPABLE is a person-centered, delivered at home by clinicians (occupational therapist [OT] and registered nurse [RN]), 20-week intervention supported by assistive devices and home modification to improve function and factors that impact function (i.e., balance, pain, depression).

The **goal** of this Stage Ib project is to examine implementation of CAPABLE in Home and Community Based Service waiver program sites (N=18) in MI. The waiver supports 15,000 low-income, nursing home eligible, disabled and older adults in the community, providing 19 services (i.e., personal care, meals, etc.) and case management through home visits by 575 clinicians (RNs and social workers [SW]). This research is premised on prior work that translated¹⁰⁻¹² CAPABLE at one site (Hartford/CMS; 2014); and pilot tested implementation strategies (MiCAP: training, facilitation, coalition building, audit and feedback) at four sites (Hillman/CMS; 2015-17).

Building on our prior work, objectives for this project are:

1. To test primary site-level outcomes of *adoption* and *sustainability* of CAPABLE after deploying MiCAP implementation strategies; and
2. To examine secondary beneficiary-level outcomes (*ADL/IADLs, pain, depression, falls, ED/hospital use*) after deploying MiCAP implementation strategies.

Work at 18 program sites will include readiness assessment, training, coalition building, audit, feedback, and facilitation. Internal facilitators (IFs) and external facilitators (EFs), who were prior work adopters of CAPABLE, will facilitate.

Testing will occur in a 3-year community-based participatory research¹³ with Hybrid-3¹⁴⁻¹⁵ mixed method trial design.¹⁶⁻¹⁸ With rolling enrollment, sites will be randomized to MiCAP with IF or MiCAP with IF+EF and baseline assessments of the characteristics of sites and clinicians will be completed. CAPABLE will be provided to beneficiaries. Clinicians (RNs/OTs/SWs) and IFs will be trained in CAPABLE. IFs and EFs will be trained in facilitation techniques. Post-implementation data, site Stages of Implementation Completion (SIC), and clinician satisfaction will be collected; an implementation fidelity checklist (including IF/EF fidelity) will be completed monthly. Clinician attitude and self-efficacy will be measured at baseline and 9 months. Beneficiary level data will be collected during usual care and includes assessment prior to and after CAPABLE and any assessments that occurred between the two time points.

The *significance* of this project is in the use of the evidence-based model, CAPABLE, in an underfunded Statewide Medicaid environment, where change is difficult to attain. This work will impact implementation science by testing two approaches to implementation of an evidence-based intervention to improve outcomes among older adults in a Medicaid waiver program. This natural setting approach has high generalizability for waiver sites, as we learn what intensity of implementation strategies is needed to adopt and sustain evidence, potentially transforming programs of care for our nation's most vulnerable older adults who are aging-in-place. This study is also significant as it addresses a critical barrier to implementation of evidence-based interventions to improve function in older adults living in the community to age-in-place (CAPABLE). The National Institute on Aging focuses on ways to improve function once considered an inevitable part of aging. Likewise, the American Association of Retired Persons, National Aging in Place Council, and National Association of Area Agencies on Aging have aging-in-place as a priority. Evidence suggest 90% of older adults prefer to age-in-place; yet a gap exists between their desire and ability.²⁹ Thus, further testing of efficacy of an intervention (CAPABLE) in a Medicaid waiver population will fill a gap in science and build evidence.

1.3 SPECIFIC AIMS

The **specific aims** are as follows.

Aim A1 To test the effects of MiCAP with IF alone versus MiCAP with IF+EF with respect to the site-level outcomes of adoption and sustainability (**primary**) and beneficiary-level outcomes of ADL/IADLs, pain, depression, falls, emergency department (ED) visits and hospitalizations (**secondary**) over the next 12 months.

Aim A2 Mechanism-of-action To determine whether the effects of EF+IF versus IF on primary outcomes are mediated by clinician attitude or self-efficacy at 9 months.

Aim A3 To benchmark the effects of IF and EF+IF on beneficiary outcomes following implementation as compared to pre-intervention.

Exploratory Aim A4 To compare the primary and secondary outcomes within 12 months, potential mediators at 9 months, and baseline leadership and readiness for sites with SIC of >50% versus sites with SIC \leq 50% at 6 months in each arm.

Exploratory Aim A5 To explore whether baseline site leadership and readiness moderate the impact of EF+IF compared to IF on primary and secondary outcomes within 12 months in order to determine which sites may require facilitation that is more intensive.

Exploratory Aim A6 To evaluate clinician satisfaction at 1 month, and the cost of implementation and policy impact for IF and IF+EF at 12 months.

The National Institutes of Health (NIH) defines Implementation Science (IS) as the process of applying evidence to the treatment or prevention of human disease.¹⁹⁻²⁰ A scientific study of methods to promote uptake of evidence into routine care to improve quality and effectiveness of healthcare through the study of influences on clinician and organizational behavior.²¹ This study is significant because it addresses testing of multimodal implementation strategies of an evidence-based intervention (CAPABLE) in a Medicaid setting to improve the quality and effectiveness of a waiver.

We will utilize implementation strategies²² refined in prior work (MiCAP; Hartford/Hillman/CMS) where we trained clinicians (N=34), modified the EHR, and provided CAPABLE for beneficiaries (N=270). We extend our work and train all RNs, OTs, and SWs (N=575) in the 18 waiver sites in MI to implement the CAPABLE model of care for all Medicaid waiver beneficiaries (N=15,000). Guided by site managers, our team will select and train Internal Facilitators (IFs), who are supervisors/employees that work for the waiver site, to conduct facilitation at each site as “Champions”. We will utilize waiver employees as the External Facilitators (EFs), who were early adopters of CAPABLE in our prior work, as “Super-Champions” for Arm 2.

Further, we focus on a topic of particular IS import: sustainability of implementation efforts.²³⁻²⁶ In a recent scoping review of 62 trials and 41 reports in the field of knowledge translation, few studies focused on sustaining interventions.²⁷ Without sustainment, true practice change may not occur and healthcare outcomes may not improve. Further, we will be one of the first to examine implementation strategy (MiCAP) mechanisms of action - awareness, commitment, confidence, and trust - identified in the work of Abramowicz and colleagues in 2016,²⁸ while implementing a complex intervention (CAPABLE).

1.4 DESIGN

This 2-arm, 3-year randomized study that will examine implementation strategies (MiCAP) to adopt and sustain CAPABLE and improve beneficiary outcomes¹⁴⁻¹⁵. The Hybrid-3 approach was selected as we will be testing implementation intervention strategies (MiCAP) while simultaneously gathering information on the evidence-based intervention (CAPABLE) and related outcomes in a new setting, the waiver program sites.¹⁵

1.5 SAMPLE

The sample includes the following groups:

1. Sites: The 18 Medicaid Waiver program sites in the State of MI.
2. Clinicians: The 575 RNs/OTs/SWs employed by the site to provide care to beneficiaries.
3. Beneficiaries: The 15,000 Medicaid beneficiaries who are recipients of care in the site.

1.6 SETTING

The setting is the MI Medicaid waiver sites.

1.7 INCLUSION AND EXCLUSION CRITERIA

Inclusion Criteria

Included are waiver sites under contract as a waiver provider in MI who use the Center for Information Management (CIM) electronic health record (EHR); clinicians employed at the site who are trained in CAPABLE; and beneficiaries who receive care from a clinician trained in CAPABLE.

Exclusion Criteria

Sites not contracted as a waiver site or those not using CIM’s EHR will be excluded.

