1.9 ORGANIZATIONS ASSOCIATED WITH THE STUDY

NIA The National Institutes of Aging funded the project (NIA 1 R15 AG058193-01A1). As such, for this study, all requirements (i.e., privacy, confidentiality, Health Insurance Portability and Accountability Act (HIPAA), IRB, budget, report, dissemination, data sharing, protocol, etc.) will be met through execution and implementation of the Notice of Award (NOA) agreement with the university.

CMS The Center for Medicare and Medicaid Services is the oversight organization of MDHHS. As such, for this study, all requirements (i.e., privacy, confidentiality, HIPAA, etc.) will be met through execution and implementation of the MDHHS IRB and DUA.

MDHHS The Michigan Department of Health and Human Services (MDHHS) is the oversight organization of all Medicaid programs for the State of Michigan, and as such, contracts with each of the waiver sites to manage, hire, or contract employees, and provide care to beneficiaries in the waiver program. As an oversight organization, MDHHS collects administrative, CQAR, and beneficiary data and has access to all current and past data of this nature. We will execute an IRB and DUA with MDHHS to perform this study.

Sites Home and Community Based Services Provider waiver program sites are under contract with State of MI MDHHS to manage, hire or contract employees, and provide care to beneficiaries in the waiver program. We will execute a contract and DUA with each site that agrees to participate to perform this study. Deployment will occur in a staged manner, with 2—4 sites each month until all are deployed.

CIM Center for Information Management (CIM) is under contract with MDHHS and 18 sites (20 years) to house and manage the EHR and billing software for the State of MI Medicaid waiver program. This platform contains beneficiary level data for all Medicaid beneficiaries in the waiver program where our study will occur.

The website (www.ciminc.com/) provides a description of CIM's mission and purpose; and contains a statement of HIPAA compliance, required by CMS and MDHSS. We will obtain a DUA. The following will occur.

1. De-identified data on beneficiaries outcomes from care by clinicians trained in CAPABLE at sites who do not opt-out will be obtained from CIM.
2. Data transfer to the university (PI/PM) will be electronic through a CIM data secure encrypted portal as the data will be de-identified.

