1.14 DATA ANALYSIS

Preliminary analysis

The distributions of outcomes, mediators, and potential covariates will be assessed, outliers will be investigated by inspecting the residuals, and models described below will be fit with and without outliers to examine their influence on the results. Analyses will be implemented in SAS 9.4 as follows:

Aim A1 To test the effects of MiCAP with IF alone versus MiCAP with IF+EF with respect to the site-level outcomes of adoption and sustainability (**primary**) and beneficiary-level outcomes of ADL/IADLs, pain, depression, falls, emergency department (ED) visits and hospitalizations (**secondary**) over the next 12 months. Primary outcomes will be analyzed using a linear mixed effects model with repeated measures: 11 monthly measures of the SIC, 11 monthly summary records of clinician's actions based on EHR documentation, and monthly for 9 months measures from IF tools (statistical model #1). Covariates will include trial arm, variables used in randomization (site's size and CQAR score), and time entered as a class variable to model potentially non-linear patterns. In addition, we will use general liner model to analyze clinicians' fidelity training data. Log-rank test and Cox proportional hazard modeling will be employed to analyze time spent in each stage (treated as censored if a site does not complete a given implementation stage). The test of significance of the coefficient of the trial arm variable will yield the formal test of hypothesis associated with this aim for the main (time-averaged) effect of IF+EF v. IF alone. The analysis of secondary beneficiary-level outcomes will employ use generalized linear model with appropriately distributed errors and the random effect of site added to account for nesting of individuals within sites. For counts of falls and health service use, Poisson error distribution will be specified. Alternatively, as a zero-inflated Poisson or negative Binomial model based on the distribution of the counts will be fit. The explanatory variables including trial arm will be evaluated as predictors of zero inflation (whether or not the count is zero), and as predictors of the magnitude of the count when it is not zero. Pre-intervention MDS assessment will be used to obtain baseline version of each outcome, which will be included as a covariate to explain the variation in post-intervention outcomes.

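### Followed as written, the Aim A1 beneficiary comparison covers only patients of CAPABLE-trained clinicians, a group formed after sites are randomised, and section 1.14 names no analysis set by randomised arm

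*Combined protocol and SAP*

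**What the plan says.** **Restriction.** Section 1.7 includes "beneficiaries who receive care from a clinician trained in CAPABLE". Section 1.9 matches it: what CIM will supply is "De-identified data on beneficiaries outcomes from care by clinicians trained in CAPABLE at sites who do not opt-out". Section 1.13 names CIM as the source of beneficiary outcomes.

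**Whole programme.** Section 1.5 describes the beneficiary sample as "The 15,000 Medicaid beneficiaries who are recipients of care in the site", with no training condition. Section 1.3 sets out to "train all RNs, OTs, and SWs (N=575) in the 18 waiver sites in MI".

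**Analysis.** For the secondary outcomes under Aim A1, section 1.14 specifies a "generalized linear model with appropriately distributed errors and the random effect of site added to account for nesting of individuals within sites". It adds that "Pre-intervention MDS assessment will be used to obtain baseline version of each outcome", to be used as a covariate. It names no analysis set and gives no rule for patients whose clinicians did not train.

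**Training.** Clinicians are invited to train and must consent (section 1.17). The measures table in section 1.12 lists fidelity to training under Adoption. Under Aim A1, section 1.14 states "we will use general liner model to analyze clinicians", meaning their training-fidelity data. Section 1.1 lists "engaging clinicians for training" among the matters on which the external facilitator (EF), present in one arm only, guides internal facilitators (IFs).

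**The concern.** Sites are randomised, so the protected comparison is between everyone at the sites in one arm and everyone at the sites in the other. Limiting beneficiaries to those with a trained clinician makes entry depend on something that happens after assignment and that the plan itself treats as an outcome of the strategies being compared.

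Two things are at stake for ADL/IADL, pain, depression, falls, ED visits and hospitalisations. If training uptake differs by arm, or if the clinicians who train bring different kinds of patients in each arm, the arms hold differently selected beneficiaries and the difference between them is no longer purely the effect of EF. In addition, any effect on patients with no trained clinician falls outside the comparison.

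**Working it through.** **1. The plan's own figures.** Section 1.15 assumes 750 beneficiaries analysed per site, ICC 0.01 and 9 sites per arm. DEFF = 1 + (750 - 1) x 0.01 = 8.49. Effective n per arm = 9 x 750 / 8.49 = 795. Detectable d = (1.960 + 0.842) x sqrt(2/795) = 0.14, taking two-sided 5% and 80% power, which the section does not state. All three published figures reproduce. Total analysed = 18 x 750 = 13,500, which is 90% of 15,000.

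**2. Order of events.** Section 1.16 pairs sites on size and CQAR score and flips a coin; training status plays no part. Section 1.2 describes randomisation before training, and the data collection table in section 1.13 puts training in month 1. No explicit date for randomisation relative to training is given, so the order is inferred. The 34 clinicians trained in earlier work (section 1.3) are an exception.

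**3. How far the two beneficiary sets can differ.** The documents give neither uptake nor the number of clinicians per beneficiary. Assume uptake p, k clinicians per beneficiary training independently, and one trained clinician sufficient. Beneficiaries in the section 1.5 set but outside the section 1.7 set = 15,000 x (1 - p)^k.

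| k | p = 0.6 | p = 0.9 |
|---|---|---|
| 1 | 15,000 x 0.4 = 6,000 | 15,000 x 0.1 = 1,500 |
| 2 | 15,000 x 0.16 = 2,400 | 15,000 x 0.01 = 150 |
| 3 | 15,000 x 0.064 = 960 | 15,000 x 0.001 = 15 |

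If team members tend to train together, the gap moves towards the k = 1 row. If all train (p = 1), it is zero apart from opt-outs.

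**4. Does the 750 show which set was meant?** Uptake needed for 90% coverage is 1 - 0.10^(1/k): 0.90 for k = 1, 0.684 for k = 2, 0.536 for k = 3. The 13,500 also fits all 15,000 less opt-outs and missing assessments. It does not discriminate.

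**5. Precision is not the problem.** If half of the 750 per site were covered, m = 375, DEFF = 1 + 374 x 0.01 = 4.74, effective n = 9 x 375 / 4.74 = 712, and detectable d = 0.148 against 0.141 for the full 750. The issue is selection.

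**6. What selection could do, on assumed inputs only.** Suppose no true effect and no baseline adjustment. Shares p1 and p2 of beneficiaries are included in the two arms, and the extra patients in the fuller arm differ by delta SD. The spurious difference is (p2 - p1)/p2 x delta.

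- 70% v 80%, delta 0.2: 0.1/0.8 x 0.2 = 0.025 SD, type I error about 0.08.
- 50% v 70%, delta 0.2: 0.2/0.7 x 0.2 = 0.057 SD, type I error about 0.20.
- Equal shares with the same patient mix: zero.

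The error rates use a normal approximation with ICC 0.01. None of these inputs comes from the documents, so these are illustrations and not estimates for this trial.

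**The case against.** **The route from arm to uptake is thin.** It rests mainly on one phrase in the definitions table. The strategy table in section 1.11 places training at the start of implementation and EF one month later. Section 1.13 schedules training in month 1. Section 1.11 has IFs encouraging training in both arms and describes EF support for work with clinicians already trained. This stands: a difference in uptake by arm is possible but not shown. It is not excluded either, because section 1.12 counts certifications monthly for 12 months and section 1.11 lists adoption among the outcomes EF affects.

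**Section 1.5 may only describe the source population,** with section 1.7 supplying eligibility. That is a fair reading, and it means the two sections need not be rival analysis sets. It does not help the comparison: if section 1.7 is the default, the conditioning on training is confirmed.

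**An effect among patients of trained clinicians is a legitimate target in a Hybrid-3 trial.** As a supportive analysis, yes. Aim A1, however, compares implementation strategies by randomised arm.

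**Baseline adjustment.** It reduces the effect of differences captured by the baseline outcome. It cannot bring back beneficiaries who were never extracted.

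**A stronger inference about lost benefit.** A reader might conclude that all EF benefit arising from extra training disappears from the beneficiary results. The documents do not support that. If one trained team member suffices for inclusion, training a second or third clinician acts on patients already counted; only effects on patients with no trained clinician are lost. The training effect itself remains visible, because training data are analysed under Aim A1.

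**Conclusion.** The point holds as a defect in how the A1 beneficiary comparison is defined. The stated eligibility and extract rules condition that comparison on a post-randomisation variable, and nothing in section 1.14 restores an analysis by randomised arm.

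It affects every secondary beneficiary outcome. The primary outcomes built on the Stages of Implementation Completion tool do not depend on the beneficiary criterion.

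A reader might go further and infer that the beneficiary results will be biased, or that EF will raise uptake in its arm. The documents give no uptake figures, and their timetable weakens that route, so the size of any bias is unknown and may be small. What can be stated is the possible gap between the sets: from 6,000 beneficiaries down to 15 across the assumed 60-90% uptake and one to three clinicians each, and none apart from opt-outs at full uptake. The conclusion rests on the inferred order of randomisation before training and on voluntary uptake being less than complete. It should be settled before CIM transfers data, which section 1.13 places at the end of each site's project period.

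**What to change.** In section 1.14, define the main A1 beneficiary set as all waiver beneficiaries at each randomised site who did not opt out and have an MDS dated before that site's start, analysed by randomised arm whether or not their clinician trained.

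Take baseline and outcome from each site's own clock, in line with the month 0 and month 12 MDS in the section 1.13 table. The Aim A3 text in section 1.14 should not be used as the model, because it dates from the start of the study. Section 1.9 deploys 2 to 4 sites a month, so 18 sites need 5 to 9 monthly waves (18/4 = 4.5, rounded up; 18/2 = 9), and study start can precede a site's start by months.

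Keep the trained-clinician subset as a supportive analysis, state whether one trained team member is enough, and report training uptake by arm beside it. Report beneficiaries who enrol after their site's start separately by arm. Reconcile sections 1.5, 1.7, 1.9 and 1.14, and widen the CIM extract. Confirm that the opt-out document, IRB approvals and data use agreements cover patients of untrained clinicians.

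**Cost.** Protocol wording and a larger extract of MDS data already collected in usual care. An IRB or data use agreement update may be needed, although the MDS items listed in section 1.8 carry no trained-clinician limit. No new data collection is required. There are two downsides: the effect is diluted if few clinicians train, and later enrollees fall outside the main comparison.
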